## 5.9 Subject Withdrawal/Discontinuation Criteria

Subjects may withdraw consent at any time for any reason or be dropped from the trial at the discretion of the investigator should any untoward effect occur. In addition, a subject may be withdrawn by the investigator or the Sponsor if enrollment into the trial is inappropriate, the trial plan is violated, or for administrative and/or other safety reasons. Specific details regarding discontinuation or withdrawal are provided in Section 7.1.4 – Other Procedures.

A subject must be discontinued from the trial for any of the following reasons:

- The subject or legal representative (such as a parent or legal guardian) withdraws consent.
- Confirmed radiographic disease progression

*Note:* For unconfirmed radiographic disease progression, please see Section 5.2.2

*Note:* A subject may be granted an exception to continue on treatment with confirmed radiographic progression if clinically stable or clinically improved, please see Section 7.1.2.7.1

- Unacceptable adverse experiences as described in Section 5.2.1.2
- Intercurrent illness that prevents further administration of treatment
- Investigator's decision to withdraw the subject
- The subject has a confirmed positive serum pregnancy test
- Noncompliance with trial treatment or procedure requirements
- The subject is lost to follow-up
- Completed 24 months of uninterrupted treatment with pembrolizumab. Administrative reasons

The End of Treatment and Follow-up visit procedures are listed in Section 6 (Protocol Flow Chart) and Section 7.1.5 (Visit Requirements). After the end of treatment, each subject will be followed for 30 days for adverse event monitoring (serious adverse events will be collected for 90 days after the end of treatment as described in Section 7.2.3.1). Subjects who discontinue for reasons other than progressive disease will have post-treatment follow-up for disease status until disease progression, initiating a non-study cancer treatment, withdrawing consent or becoming lost to follow-up. After documented disease progression each subject will be followed by telephone for overall survival until death, withdrawal of consent, or the end of the study, whichever occurs first.

Note: The treatment plan is for approximately 12 pembrolizumab infusions (36 weeks) treatment.

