## 8.1 STATISTICAL ANALYSIS PLAN

### 8.2 Statistical Analysis Plan Summary

Overall response rate (ORR) and the 95% confidence interval of that estimate will be obtained through binomial distribution theory, using the ITT population, with a one-sided endpoint, for the primary endpoint. Progression free survival, overall survival, landmark one-year progression free survival, landmark one-year overall survival will be obtained by Kaplan-Meier method.

The adverse events will be tabulated descriptively, by grade. All AEs will be summarized by system organ class and preferred term. Listings and summary tables will be provided. Separate data listings and summaries will be presented for all serious adverse events (SAEs) and deaths.

The correlative study tests will be analyzed as an exploratory assessment, or as part of a separate correlative protocol.

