#### 8.4 Planned primary reporting analyses

Analysis: Overall response rate ORR is defined with confirmation of the response status CR or PR among the combination treatment population patients; the binomial estimate and its one-sided 95% confidence interval will be reported.

Analysis: Overall survival (OS) of ITT patients counting from the eligible date to death from any cause, or censored on end of known follow up, either within this study or in the PROCLAIM registry.

Analysis: Progression-free survival (PFS) of ITT patients from the confirmed eligible date to the first occurrence of disease progression or death, from any cause, or lost to follow up, whichever is earliest; or censored at last follow-up during study.

Kaplan-Meier method will be used for OS as well as PFS analysis.

The Simon minimax two-stage design (Simon, 1989) with a 10% type I error and 90% power will be used to test the null hypothesis that overall response rate (CR+PR)  $\leq 0.20$  versus the alternative hypothesis of overall response rate  $>0.45$ . In the 1st stage, 15 patients will be treated. If 3 or fewer respond, the trial will be terminated. If 4 or more respond, an additional 9 evaluable patients (the “combination treatment population”) will be studied in the 2nd stage (a total of  $n=24$  evaluable patients). If the total number responding is less than or equal to 7, the drug is rejected. This design has an expected sample size of 18 patients with a probability of early termination of 0.65.

The overall total number of patients, counting patients with at least one dose of IL-2 administered, will be up to  $n =26$ . This will accommodate replacement of subjects who are in the intent-to-treat(ITT) population, but not part of the main developmental objective of the study, which is the combination treatment population.

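### The PFS definition lists loss to follow-up as an endpoint and also censors at last follow-up, so a patient lost without progression meets both rules

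*Combined protocol and SAP*

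**What the plan says.** Section 8.4 defines PFS for the ITT population, from the confirmed eligible date to the "first occurrence of disease progression or death, from any cause, or lost to follow up, whichever is earliest". The sentence as a whole ends "or lost to follow up, whichever is earliest; or censored at last follow-up during study", and the clause after the semicolon does not say which patients it covers.

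The OS definition just above it has a different structure: time runs to "death from any cause, or censored on end of known follow up, either within this study or in the PROCLAIM registry". Death is the only event, and the end of known follow-up is censored.

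For the estimator, Section 8.4 says "Kaplan-Meier method will be used for OS as well as PFS analysis", and Section 8.2 adds that "landmark one-year progression free survival, landmark one-year overall survival will be obtained by Kaplan-Meier method".

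Section 5.9 foresees that patients will be lost. One of its reasons for discontinuing a subject is "The subject is lost to follow-up", and post-treatment disease follow-up for patients who stop without progression runs "until disease progression, initiating a non-study cancer treatment, withdrawing consent or becoming lost to follow-up". Neither statement gives a PFS code.

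**The concern.** Kaplan-Meier takes one time and one status, event or censored, for each patient. A patient lost without documented progression fits the endpoint list (lost, and nothing earlier) and also fits the censoring clause (there is a last follow-up date). The plan thus gives two statuses for the same patient.

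A programmer who follows the list as written will code these losses as events. The result is no longer PFS but time to progression, death or dropout, and the estimate lies below PFS whenever someone is lost. With about 26 patients, two or three such codes can visibly move the curve and the one-year landmark. In an open-label trial the coding should be settled before the analyst can see which choice gives which curve.

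**Working it through.** **Step 1: the wording.**

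| | Events | Censoring |
|---|---|---|
| OS (8.4) | Death | End of known follow-up |
| PFS (8.4) | Progression, death, loss to follow-up | Last follow-up during the study |

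Loss appears on the event side for PFS only. Sections 5.9, 7.2.3.3 and 8.2 do not resolve it.

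**Step 2: inputs for the size.** The plan states no PFS estimate, event count, power or loss rate for this trial, so it has no PFS figure to reproduce.

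- From the documents: up to 26 patients (Sections 1.0 and 8.4), and a median PFS of 4.6 months from the cited nivolumab trial (Section 4.4.4). The second is an illustrative value, not a design assumption of this trial.
- Assumed: one-year PFS of 35% or 50%; loss hazard μ of 0.1 or 0.2 per year; constant hazards; loss independent of progression and death.

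**Step 3: formulas.** Let λ be the yearly hazard of progression or death.

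- Losses censored: S(1) = exp(−λ).
- Losses as events: S(1) = exp(−(λ + μ)), which is the censored value times exp(−μ). The multipliers are exp(−0.1) = 0.9048 and exp(−0.2) = 0.8187.
- Proportion lost within the year before any event: μ/(λ + μ) × [1 − exp(−(λ + μ))].

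The hazards are −ln(0.35) = 1.050, −ln(0.50) = 0.693, and ln 2 × 12/4.6 = 1.808, the last giving exp(−1.808) = 16.4%.

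| One-year PFS, losses censored | μ | Losses as events | Fall (points) | Lost in year 1 |
|---|---|---|---|---|
| 35% | 0.1 | 0.35 × 0.9048 = 31.7% | 3.3 | 5.9% |
| 35% | 0.2 | 0.35 × 0.8187 = 28.7% | 6.3 | 11.4% |
| 50% | 0.1 | 0.50 × 0.9048 = 45.2% | 4.8 | 6.9% |
| 50% | 0.2 | 0.50 × 0.8187 = 40.9% | 9.1 | 13.2% |
| 16.4% (4.6-month median) | 0.1 | 0.164 × 0.9048 = 14.8% | 1.6 | 4.5% |
| 16.4% (4.6-month median) | 0.2 | 0.164 × 0.8187 = 13.4% | 3.0 | 8.6% |

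The proportion lost differs between rows with the same μ, because patients who progress sooner have less time in which to be lost.

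**Step 4: cross-check.** Take an assumed median of 9 months and set the one-year loss probability, in the absence of progression, at 5%, 10% and 20%. One-year PFS of 39.7% then becomes 37.7%, 35.7% and 31.7%. A Kaplan-Meier simulation with 26 patients and 5,000 runs gave 39.5% to 39.8% with losses censored, and 37.5%, 35.8% and 31.9% with losses as events.

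**Step 5: scale.** With 26 patients, one-year PFS of 35% and no censoring, the standard error is √(0.35 × 0.65/26) = 0.094, or 9.4 points. The shifts of 3.3 and 6.3 points are smaller than one standard error, but they always go in the same direction.

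**The case against.** The sentence can be read charitably. Loss to follow-up may have been meant as the end of observation, with the last clause supplying its censored status, or that clause may have been meant for patients still followed when the study closes. The neighbouring OS definition makes such an intention plausible. This stands as far as intention goes: bias is not certain. It arises only if losses are coded as events and only if someone is lost. The text does not state the charitable reading, however, and its literal list points the other way.

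PFS also decides nothing. It is absent from the objectives in Sections 3.2 to 3.4, it has no hypothesis or threshold, and the go/no-go rule is the two-stage design on response rate. Section 4.4.4.1 says that PFS cannot be analysed definitively in this trial. All of this stands and limits the consequence.

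A reader might infer that the definition spoils a comparison with historical PFS. The documents do not support that. The only PFS value they cite, the 4.6-month median, is used to justify the six-dose pembrolizumab threshold, and the same part of Section 4.4.4 says that those trials' patients are not expected to be directly comparable. No PFS comparison is planned, and the narrative synopsis already describes cross-trial comparison as limited.

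Finally, censoring is the right benchmark only if loss is non-informative. If patients drop out because they are deteriorating, censoring overstates PFS. That is a reason for a labelled sensitivity analysis, not for leaving the main rule with two answers.

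**Conclusion.** The point holds as a defect in the written definition. A patient lost without progression is assigned both an event and a censored status, and nothing in the document chooses between them. Coded as literally written, Kaplan-Meier PFS and landmark one-year PFS are too low relative to censoring under non-informative loss.

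Under constant, independent hazards and assumed loss hazards of 0.1 to 0.2 per year, the fall at one year is about 3 to 6 points from 35%, 5 to 9 points from 50%, and 1.6 to 3.0 points at a 4.6-month median. It is zero if nobody is lost. These are illustrations, since the documents give neither a loss rate nor an expected PFS. A reader might also infer that the trial's conclusion is at risk; it is not, because the response-rate rule does not use PFS. The correction is still worth making, because PFS and its one-year landmark are to be reported and the definition cannot be programmed unambiguously.

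**What to change.** Replace the PFS sentence in Section 8.4 with a rule along these lines: PFS is the time from the confirmed eligible date to the first of progression or death from any cause; patients with neither event, including those lost to follow-up, are censored at one named date, such as the last evaluable tumor assessment.

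Naming the date is a separate choice from removing loss from the event list, but it belongs in the same edit. Under Sections 7.1.1.5.3 and 7.2.3.3, patients who start new therapy move to survival contact, which may be by telephone, so a last follow-up date can fall well after the last scan.

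Counting loss as an event may be kept as a labelled sensitivity analysis. The cost is one sentence in the SAP, settled before the PFS analysis is run; the sample size, the visits and the response-rate design are unaffected.

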#### 5.3.3 Immune-related response criteria (irRC)

The irRC are the measurement of overall tumor burden as a metric of disease progression, as compared to the limitation to baseline lesion measurements taken with WHO and RECIST. According to irRC, new lesions do not constitute disease progression if net tumor burden (including new lesions) is stable or decreases. The irRC also permit disease progression prior to response and introduce the concept of confirmation of progression at a subsequent time point after first detection. This accounts for the period required for activated T-cells to infiltrate the tumor, which may cause initial tumor volume increase but can subsequently translate into tumor shrinkage. The irRC also classify durable stable disease as clinical activity. (Wolchok et al., 2009)

Note: irRECIST will be used for the primary response tabulations.

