### 5.3.4 Overall Response According to Immune-related response criteria (irRC)

FIGURE 5: *irRC SUMMARY*

|                                                      | irRC                                                                                                                                        |
|------------------------------------------------------|---------------------------------------------------------------------------------------------------------------------------------------------|
| New, measurable lesions (i.e. $\geq 5 \times 5$ mm)  | Incorporated into tumor burden                                                                                                              |
| New, nonmeasurable lesions (i.e., $< 5 \times 5$ mm) | Do not define progression (but preclude irCR)                                                                                               |
| Non-index lesions                                    | Contribute to defining irCR (complete disappearance required)                                                                               |
| Complete Response (CR)                               | Disappearance of all lesions in two consecutive observation not less than 4 weeks apart                                                     |
| Partial Response (PR)                                | $\geq 50\%$ decrease in tumor burden compared with baseline in two observations at least 4 weeks apart                                      |
| Stable Disease (SD)                                  | 50% decrease in tumor burden compared with baseline cannot be established nor 25% increase compared with nadir                              |
| Progressive Disease (PD)                             | At least 25% increase in tumor burden compared with nadir (at any single time point) in two consecutive observations at least 4 weeks apart |
| Near Complete Response (Near CR)                     | Reduction in tumor by $> 90\%$ and no new lesions in two consecutive observations not less than 4 weeks apart.                              |
| Unknown (UN):                                        | Assessment of target lesions cannot be made due to insufficient or unevaluable data. In this case, a concise explanation must be given.     |

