#### **7.1.1.5.3 Subsequent Anti-Cancer Therapy Status**

The investigator or qualified designee will review all new anti-neoplastic therapy initiated after the last dose of trial treatment. If a subject initiates a new anti-cancer therapy within 30 days after the last dose of trial treatment, the 30 day Safety Follow-up visit must occur before the first dose of the new therapy. Once new anti-cancer therapy has been initiated the subject will move into survival follow-up.

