#### ***Survival Follow-up***

Once a subject experiences confirmed disease progression or starts a new anti-cancer therapy, the subject moves into the survival follow-up phase and should be contacted by telephone or other conventional communication method every 3 months to assess for survival status until death, withdrawal of consent, or the end of the study, whichever occurs first.

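### Section 8.4 does not say whether PFS progression must be confirmed; if it must, a patient who switches therapy after one progression scan has no progression event and one-year PFS reads too high

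*Combined protocol and SAP*

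**What the plan says.** Section 8.4 runs PFS in the ITT population from the confirmed eligible date "to the first occurrence of disease progression or death, from any cause, or lost to follow up, whichever is earliest". The same sentence ends with the censoring rule: "whichever is earliest; or censored at last follow-up during study". It does not mention new anti-cancer therapy or unconfirmed progression, and it does not say whether last follow-up means the last scan or the last contact. Section 8.2 adds a Kaplan-Meier estimate of PFS at one year.

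Progression is defined in one place, Figure 5 of section 5.3.4: "At least 25% increase in tumor burden compared with nadir (at any single time point) in two consecutive observations at least 4 weeks apart". Section 5.3.3 explains that the immune-related criteria "introduce the concept of confirmation of progression at a subsequent time point after first detection". It names irRECIST for the response tabulations and names no criteria for PFS.

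Three places govern follow-up:
- Section 5.9 follows patients who stop for reasons other than progression "until disease progression, initiating a non-study cancer treatment, withdrawing consent or becoming lost to follow-up".
- Section 7.1.1.5.3 says: "Once new anti-cancer therapy has been initiated the subject will move into survival follow-up".
- Under Survival Follow-up (section 7.2.3.3), confirmed progression and new therapy are alternative routes into that phase, in which patients "should be contacted by telephone or other conventional communication method every 3 months".

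For unconfirmed progression, section 5.9 refers the reader to section 5.2.2. Two sections carry that number (inclusion criteria; timing of dose administration), and neither addresses it.

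**The concern.** Each rule is ordinary alone, but together they leave a gap. A patient whose scan shows a 25% increase, and who starts another drug before a second scan, has not progressed under Figure 5 and then leaves tumour follow-up. With confirmed progression as the event, that patient counts as progression-free beyond the progression scan. Censoring of this kind is informative, because it is triggered by the very growth that PFS is meant to record.

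The stake is the credibility of one-year PFS. PFS stands under the planned primary reporting analyses of 8.4, section 4.5 lists it among the measures that could support further development, and control is historical (section 1.0), so the figure would be read against other series. In an open-label single-arm trial, the choice between first-detected and confirmed progression should not be left until results are visible.

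**Working it through.** **The plan's own figure.** The only sized analysis is the Simon design for response rate (3/15, then 7/24; 0.20 against 0.45). It reproduces: exact type I error 0.0835, power 0.9001, early-termination probability 0.648 (plan: 0.65), expected sample size 18.17 (plan: 18). None of this concerns PFS, for which the plan gives no target or event count.

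**Inputs.** From the documents: up to 26 patients; scans at the end of each 9-week block and at one year (section 5.3); and one PFS median, 4.6 months, for nivolumab against everolimus (rationale for the half-dose threshold, section 4.4.4). At a constant hazard that median gives one-year PFS of 0.5^(12/4.6) = 0.164. Assumed: f, the share of progressors who switch before a second scan (10% to 50%); reference one-year rates of 30%, 40% and 50%; scans at weeks 9, 18, 27, 36, 44 and 52; and, for the second rule below, median survival of 24 months after the switch.

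**Formula if switchers are censored at their progression scan.** Let q be the chance of progressing between two scans. All patients still in tumour follow-up are at risk at the scan, but only a share 1 − f of progressors are events, so each Kaplan-Meier factor changes from 1 − q to 1 − q(1 − f).

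Example, reference 30%, f = 20%:
- Weekly hazard = −ln(0.30)/52 = 0.02315.
- Over 9 weeks q = 1 − exp(−0.2084) = 0.1881; over 8 weeks q = 1 − exp(−0.1852) = 0.1691.
- All first progressions counted: 0.8119⁴ × 0.8309² = 0.300.
- Switchers censored: (1 − 0.8 × 0.1881)⁴ × (1 − 0.8 × 0.1691)² = 0.8495⁴ × 0.8647² = 0.389.

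**Simulation** (1,500 trials of 26 patients per setting). One-year PFS in %, switchers censored at the progression scan / switchers event-free until death:

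| Reference | f = 10% | f = 20% | f = 30% | f = 50% |
|---|---|---|---|---|
| about 16 (median 4.6 months) | 19.4 / 22.5 | 24.5 / 30.1 | 30.2 / 37.3 | 43.5 / 51.2 |
| 30 | 34.0 / 35.7 | 38.8 / 41.7 | 44.4 / 48.0 | 56.9 / 59.8 |
| 40 | 44.0 / 45.0 | 48.5 / 50.0 | 53.4 / 55.3 | 64.2 / 65.4 |
| 50 | 53.7 / 54.2 | 57.9 / 58.6 | 62.2 / 62.9 | 71.7 / 71.4 |

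Under the first rule the shift from each setting's own simulated reference is about 4 points at 10%, 8-9 at 20%, 12-14 at 30% and 21-27 at 50%. Under the second it is similar or larger in nearly every setting.

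**Cross-check.** With continuous observation and 10% of the PFS hazard due to death, one-year PFS = exp(−H(0.1 + 0.9(1 − f))), where H = −ln(reference). For reference 30% (H = 1.204) this gives 33.4%, 37.3%, 41.5% and 51.6%: smaller shifts, same direction.

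**Scale.** At n = 26 and a true rate of 40%, the 95% half-width is about 1.96 × √(0.4 × 0.6/26) = 0.188, or 19 points. The shift at low f is well inside that, but a confidence interval does not reflect bias.

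**The case against.** **The text may already mean first detection.** Section 8.4 says first occurrence and omits the word confirmed, which the authors do use for response rate in 8.4, for discontinuation in 5.9 and for survival follow-up. Figure 5 is not expressly assigned to PFS. On this reading the shift is zero. That stands as a reasonable reading. It does not settle the matter, because under Figure 5 a single scan is not progression and no other definition is printed.

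**A confirming scan may exist.** The flow chart, as printed, shows imaging at the safety visit, and section 7.1.1.5.3 requires that visit before any new therapy begun within 30 days of the last dose. Section 5.3.2 allows extra scans on suspicion of progression. This could lower f, but not reliably. Columns may have shifted in the table, and the timing has two anchors. Section 7.2.3.3 counts about 30 days from the last dose; after a week 7 dose and a week 9 scan 14 days later, that is 30 − 14 = 16 days after the scan, short of 4 weeks. The flow chart counts 30 days from the discontinuation visit, which could be long enough.

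**Deaths still count.** Survival is followed after a switch, so some switchers become late events rather than censored ones. That is correct, but the second figure in each table cell shows that it does not remove the bias.

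**Loss to follow-up works the other way.** Read literally, 8.4 makes it a PFS endpoint, which lowers PFS. It does not cover switchers, who remain under survival contact, but it means that the net direction of error in reported PFS is not established.

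**Little depends on PFS.** It is in neither the primary nor the secondary objectives (sections 3.2 and 3.3), and section 4.4.4.1 concedes that it cannot be analysed definitively here. This stands.

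**Conclusion.** The gap is real and its effect conditional. If 8.4 means confirmed progression, one-year PFS is biased upward by one-scan progressors who switch; if it means first-detected progression, this bias is absent; the plan does not say which. The size cannot be derived from the documents. The shifts of roughly 4, 8-9, 12-14 and 21-27 points rest on assumed switching fractions of 10%, 20%, 30% and 50%, a constant hazard, and switching unrelated to speed of progression. They may be smaller if the safety-visit scan supplies confirmation.

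A reader might infer that the plan censors all these patients, that reported PFS is certainly inflated, or that the fastest progressors are the ones removed. The documents do not support that: censoring follows from a missing rule rather than a stated one, later deaths count, loss to follow-up pulls the other way, and nothing in the documents or in these calculations links switching to speed of progression. The response-rate test and its go/no-go rule are unaffected. The correction is worth making, but the trial's main decision does not depend on it.

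**What to change.** Amend the PFS definition in section 8.4:
- Date progression at the first scan that meets the 25% criterion.
- Count it as an event if confirmed, or if no later evaluable scan exists because the patient started new therapy, left the study or died. Do not count it if a later scan refutes it.
- Censor all other patients without an event at the last tumour assessment, not the last contact. This includes patients lost to follow-up, who should no longer be listed as an endpoint, and patients who start new therapy without a qualifying scan. Death remains an event.
- Add one sensitivity analysis that counts the start of new therapy as an event.

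The cost is SAP wording and one further Kaplan-Meier run. Sections 7.1.1.5.3, 7.1.2.6 and 7.2.3.3 already provide for the imaging and subsequent-therapy data, and no treatment rule changes. Reported PFS may be somewhat less favourable. An occasional pseudoprogression, the early growth before shrinkage for which section 5.3.3 introduces confirmation, may be counted as an event when no later scan is available to refute it.

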#### ***Follow-up Visits***

Subjects who discontinue trial treatment for a reason other than disease progression will move into the Follow-Up Phase and should be assessed as clinically indicated by radiologic imaging to monitor disease status, usually about every 2-3 months during the first year. After 1 year, usually every 3 months. Every effort should be made to collect information regarding disease status until the start of new anti-neoplastic therapy, disease progression, death, end of the study. Information regarding post-study anti-neoplastic treatment will be collected if new treatment is initiated.

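### Section 8.4 does not tie the PFS censoring date to a tumor assessment, so read literally it counts time after a switch of therapy without progression as progression-free

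*Combined protocol and SAP*

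**What the plan says.** **PFS rule (Section 8.4).** PFS in the ITT population starts when eligibility is confirmed. Its end is worded as "to the first occurrence of disease progression or death, from any cause, or lost to follow up". For the timing, and for patients with no such occurrence, the sentence then reads "whichever is earliest; or censored at last follow-up during study". The rule does not name the last tumor assessment and does not mention new anti-cancer therapy. The OS rule in the same section censors at the end of known follow-up, in the study or in the PROCLAIM registry.

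**Summaries (Section 8.2).** Kaplan-Meier estimates include "landmark one-year progression free survival".

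**What happens when a patient switches therapy.**
- Section 7.1.1.5.3: "Once new anti-cancer therapy has been initiated the subject will move into survival follow-up".
- Survival Follow-up (under 7.2.3.3): "Once a subject experiences confirmed disease progression or starts a new anti-cancer therapy, the subject moves into the survival follow-up phase". Contacts are made "every 3 months to assess for survival status until death, withdrawal of consent, or the end of the study". The flow chart in Section 6.1 allows these by telephone and has no imaging mark in the survival follow-up column.
- Follow-up Visits (under 7.2.3.3): "Every effort should be made to collect information regarding disease status until the start of new anti-neoplastic therapy". Section 5.9 also ends disease-status follow-up when a non-study cancer treatment begins.

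**Passages that point the other way.** Section 5.3 schedules tumor assessments at the end of each block and at 1 year. Section 7.1.2.6 schedules imaging about every 2 to 3 months through 1 year after the treatment cycles. Neither names an exception for patients on new therapy.

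**The concern.** Survival follow-up is follow-up during the study, and a patient can enter it without progression. If that patient's PFS is censored at the last contact of any kind, the risk set includes months in which nobody was required to look for progression.

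Take a patient with a last scan at month 4, new therapy at month 5, no later imaging, and a telephone contact at month 18 confirming the patient is alive. Read literally, PFS is censored at 18 months and the patient is progression-free at the one-year landmark, although disease status is unknown after month 4. A switcher who dies during survival follow-up likewise counts as progression-free until death.

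Such patients are foreseeable. Table 3 requires permanent discontinuation for several toxicities, treatment ends at about 36 weeks with no retreatment, and the protocol plans to record later anti-cancer therapy. The control is historical (Section 1.0), so no concurrent arm carries the same distortion. A raised one-year PFS would pass straight into any cross-trial comparison.

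**Working it through.** **1. The plan's own figures.** PFS has no stated sample size, event count or power. The only design figures in 8.4 are for the Simon ORR design (at most 3 of 15 stops; at most 7 of 24 rejects), and they reproduce:
- Early termination at a rate of 0.20: P(X ≤ 3 | 15, 0.20) = 0.648 (stated 0.65).
- Expected size: 15 + 9 × (1 − 0.648) = 18.17 (stated 18).
- Exact type I error 0.0835 (limit 0.10); power at 0.45 is 0.9001 (stated 90%).

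None of these uses a PFS date.

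**2. Small worked case.** Assume 26 patients, 5 events before month 4, 8 more by month 12, and switchers last scanned at month 4 and still alive by telephone after month 12.
- Literal rule, any number of such switchers: 13/26 = 50.0%.
- One switcher censored at the scan: (21/26) × (12/20) = 48.5%, a difference of 1.5 points.
- Three switchers censored at the scan: (21/26) × (10/18) = 44.9%, a difference of 5.1 points.

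No single switcher can move the estimate by more than 1/26 = 3.8 points.

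**3. Simulation.** The documents give no rate of switching without progression, so every input here is an assumption except the 4.6-month median. That is the nivolumab PFS median cited in the rationale for assessing half the planned doses (under 4.4.4). Assumptions: exponential PFS, switching between months 3 and 9, median survival 24 months after a switch, 18 months of follow-up, scans every 9 weeks, and 400,000 simulated patients per setting. True one-year PFS is 2^(−12/median): 16.4% at 4.6 months and 39.7% at 9 months.

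| Median PFS | Switch without progression | Literal | True | Shift (points) |
|---|---|---|---|---|
| 4.6 months | 4% | 18.3% | 16.4% | 1.9 |
| 4.6 months | 8% | 20.2% | 16.4% | 3.8 |
| 4.6 months | 13% | 21.9% | 16.4% | 5.5 |
| 9 months | about 12-13% | 42.3% | 39.7% | 2.6 |

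The lowest-switching setting at a 9-month median gave 41.0%, a shift of 1.3 points. A repeat run at 4.6 months and 8% gave 19.9%. Censoring at the last scan gave 15.6% to 16.2% at 4.6 months and about 39.0% at 9 months, each within about 1 point of the true value and slightly below it.

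**4. Wider assumptions.** A second simulation used time-to-progression medians of 4.6 to 12 months, median OS of 24 or 36 months, and 6% to 27% actually switching. The gap between the literal rule and last-scan censoring ran from 36.6 − 35.2 = 1.4 points to 27.9 − 11.5 = 16.4 points. The upper end needs more than a quarter of patients to switch without progression, and nothing in the documents supports that share.

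**5. Against sampling error.** The approximate 95% half-width with 26 patients and no censoring is 1.96 × √(p(1 − p)/26). That is 14.2 points at p = 0.164 and 18.8 points at p = 0.397.

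**The case against.** **The term is undefined.** Last follow-up during the study could mean the last disease follow-up. The protocol separates Follow-up Visits, which carry imaging, from Survival Follow-up, and 8.4 words the OS rule differently. This stands: a reader might infer that the plan definitely censors at the last telephone contact, and it does not say that. It does not choose the scan date either, so the rule permits two dates and one of them is biased.

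**Imaging may continue.** Sections 5.3 and 7.1.2.6 schedule imaging to 1 year, and 7.2.3.3 has visits every 2 to 3 months through 24 months, without exempting switchers. This also stands in part. Some switchers may be scanned at 1 year, so it is too strong to say that progression could not be seen. But 5.9 and Follow-up Visits end disease-status collection at the switch, so assessment after it is not systematic.

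**Overall direction.** A reader might infer that the PFS rule as a whole is biased upward. The documents do not support that. The same sentence lists loss to follow-up beside progression and death. Read as an event, it pushes PFS down. The upward direction holds for switchers only.

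**Consequence.** PFS appears in no objective in Sections 3.2 to 3.4 and has no test or decision rule, and 4.4.4.1 says it does not lend itself to definitive analysis in this trial. That is correct and limits the weight of the point. PFS is still listed under the planned primary reporting analyses, and Section 4.5 names it as a possible basis for further development.

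**Conclusion.** The point holds as a defect in the censoring rule for one group: patients who start new anti-cancer therapy with no documented progression. The literal reading counts time without systematic assessment as progression-free and raises Kaplan-Meier and one-year PFS for them. With 4% to 13% switching, the shift in one-year PFS is about 1 to 6 points. That rests wholly on assumed switching and survival patterns, is small below about 5% switching, and lies well inside the sampling error.

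A reader might infer that the trial's conclusion is at risk. It is not: the ORR boundaries do not use PFS, and patients who progressed before switching already have their event. The change is still worth making before analysis, because the bias is avoidable at almost no cost.

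**What to change.** In Section 8.4, replace the PFS censoring clause with a rule to this effect:
- Patients without progression or death are censored at their last evaluable tumor assessment, or at the eligible date if there is no post-baseline scan.
- Patients who start non-study anti-cancer therapy before progression are censored at their last tumor assessment on or before the start of that therapy, including those who die later.
- The end of known follow-up remains the censoring date for OS only.

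A sensitivity analysis may count the start of new therapy as a PFS event, since patients who switch may not be a random subset and censoring them is itself an assumption. The role of loss to follow-up in the same sentence needs its own clarification.

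**Cost.** Wording only. Imaging and post-study therapy are already recorded, and design, sample size and patient care do not change. Reported PFS becomes slightly less favourable. In the 4-13% settings, last-scan censoring fell up to about 1 point below the true value.
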